7.1 Source Data Documentation

The investigator will maintain source documents for each patient in the study (hospital or clinical medical records) containing demographic and medical information. All information relevant to a participant's general medical history on CRFs must be traceable to these source documents in the patient's case notes.

The study CRF's and patient questionnaires will be used as source data but data relevant to a participant's general medical history will be recorded also in the electronic case notes.

All source data documents are detailed separately to the protocol.

Case Report Forms

Electronic data collection will be set up by the ECTU using local software.

8 DATA MANAGEMENT

8.1 Personal Data

Patient details (including name, address, telephone number, email address, age, sex, CHI/NHS number, Body Mass Index, relevant medical/surgical history and treatments) will be collected as part of this trial and to facilitate the central follow-up and Process Evaluation (only applicable for those that consent for their details to be shared with the

Process Evaluation Team). Personal data will be stored by the research team on University of Edinburgh secure servers. Personal data will be stored for a minimum of 10 years after the study end date to permit data linkage.

8.2 Data Information Flow

No data will be sent outside the UK.

8.3 Transfer of Data

Data collected or generated by the study (including personal data) will not be transferred to any external individuals or organisations outside of the Sponsoring organisation(s).

8.4 Data Controller

A data controller is an organisation that determines the purposes for which, and the manner in which, any personal data are processed.

The University of Edinburgh and NHS Lothian are joint data controllers along with any other entities involved in delivering the study that may be a data controller in accordance with applicable laws (e.g. the site)

8.5 Data Breaches

Any data breaches will be reported to the University of Edinburgh and NHS Lothian Data Protection Officers who will onward report to the relevant authority according to the appropriate timelines if required.

9 STATISTICS, DATA ANALYSIS AND PROCESS EVALUATION

9.1 Sample size calculation

The minimally clinically important difference (MCID) for the primary outcome measure is 8-10 (see KOOS website www.koos.nu), so we have used a value of 9, the mid-point of this range. To account for 20% unidirectional crossover from the non-surgical arm to the surgical arm, we have used an MCID of 7.2. If the observed treatment effect was going to be 9, then the observed mean KOOS in one arm would have been x , and in the other arm it would have been $x+9$. If there is 20% cross-over in one direction, and you analyse by intention-to-treat, then the observed mean KOOS in one arm is now still x , and in the other arm it is now $[0.8(x+9) + 0.2x] = x+7.2$. We have assumed the standard deviation for the KOOS will be 15 (13,41,42,43,44,45). To account for and adjusting for baseline KOOS, we have assumed a correlation between baseline and follow up measurement of 0.25. This reduces the standard deviation to 13. $\text{Variance}_2 = (1-\rho^2) \text{variance}_1$ where $\text{variance}_1 = 15^2$, and $\rho = 0.5$ (From pg54 Julious, Sample sizes for clinical trials). Therefore new $\text{SD} = \sqrt{168.75} \approx 13$. The intracluster correlation coefficient of the KOOS amongst surgeons is likely to be around 0.056 (60). Using this value, and assuming there will be approximately 5 patients per surgeon, gives a design effect of 1.224. [design effect = $1 + (0.056 * (5-1)) = 1.224$]. We have adjusted for clustering among surgeons through multiplying by the square root of the design effect (1.106) to obtain a standard deviation in the surgical arm of 14.4. In the non-surgical intervention arm of the trial, the number and variety of physiotherapists treating each patient is variable, and clustering by physiotherapist is not appropriate.

However, the components of the non-surgical intervention are likely to be similar with each centre, and vary between centres, so clustering on centre within the non-surgical intervention arm is more appropriate. We have assumed that the intracluster correlation coefficient of the KOOS in the non-surgical intervention arm of each centre is 0.056. If there are 10 patients per centre, we get a design effect of 1.504. [design effect = $1+(0.056*(10-1)) = 1.504$]. We have adjusted for clustering in the physiotherapy arm through multiplying by the square root of the design effect (1.226) to obtain a standard deviation in the physiotherapy arm of 15.9. Using 90% power, 2-sided $p=0.05$, with a difference of 7.2, and standard deviations of 14.4 and 15.9, this gives a sample size of 95 per group. Allowing for 15% loss to follow up gives 112 per group.

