4 STUDY POPULATION

4.1 Number of participants

A total of 224 patients (112 in each arm) will to be recruited from approximately 20 UK sites over a 24-month period.

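### The PKT design effect assumes 10 patients per centre, but 112 PKT patients over about 20 sites average 5.6; the mismatch is conservative and needs reconciling in the text

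*Protocol*

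**What the plan says.** Section 9.1 starts from a KOOS standard deviation of 15 ("We have assumed the standard deviation for the KOOS will be 15") and allows for baseline KOOS ("This reduces the standard deviation to 13"). It then inflates each arm separately for clustering.

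- **Surgical arm:** the cluster is the surgeon, with an ICC of 0.056 and a cluster size given as "assuming there will be approximately 5 patients per surgeon". The design effect is 1.224 and the SD 14.4.
- **PKT arm:** the cluster is the centre, counted within that arm only, with the same ICC. "If there are 10 patients per centre, we get a design effect of 1.504", and the SD becomes 15.9.

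The result follows: "Using 90% power, 2-sided $p=0.05$, with a difference of 7.2, and standard deviations of 14.4 and 15.9, this gives a sample size of 95". That number applies to each arm and is raised to 112 for 15% loss to follow-up.

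Section 4.1 gives the recruitment plan: "A total of 224 patients (112 in each arm) will to be recruited from approximately 20 UK sites". Section 3 gives 1:1 allocation. The protocol does not explain the 10, does not mention unequal centre sizes, and gives no number of surgeons.

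**The concern.** Section 9.1 defines the PKT cluster as the patients of one arm at one centre, so the cluster size in the design effect has to be PKT patients per centre. The recruitment plan puts that mean at 5.6, a little over half of the 10 used. The design effect of 1.504, the SD of 15.9, the 95 per group and the 112 per group all depend on the 10.

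At stake is whether the stated power describes the trial laid out in section 4.1. Section 9.2 also points back to the sample size calculation for how clustering will be handled, so the description there should match the planned design.

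**Working it through.** **Inputs.** From section 9.1: 90% power, two-sided 5%, difference 7.2, adjusted SD 13, ICC 0.056 in both arms, 5 patients per surgeon, 10 PKT patients per centre, 15% loss. From section 4.1: 112 per arm and about 20 sites.

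**Formulas.**
- Design effect DE = 1 + ICC × (m − 1)
- Arm SD = 13 × √DE
- Normal approximation: n per group = (SD₁² + SD₂²)(1.960 + 1.282)² / 7.2². The t-based (Welch, noncentral t) version adds one or two patients.
- Randomised per group = n / 0.85, rounded up

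**1. The protocol's own figures.**
- Surgical arm: 1 + 0.056 × 4 = 1.224; 13 × √1.224 = 14.38, stated as 14.4.
- PKT arm: 1 + 0.056 × 9 = 1.504; 13 × √1.504 = 15.94, stated as 15.9.
- Sample size: with 14.4 and 15.9 the normal approximation gives 93.3, so 94. The t-based version gives 95.
- Loss: 95/0.85 = 111.8, so 112.

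Every stated figure reproduces. The question is only the input of 10.

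**2. Cluster size implied by section 4.1.**
- Randomised: 112/20 = 5.6 PKT patients per centre.
- Analysed: 95/20 = 4.75.
- Sites needed for 10 PKT patients each: 112/10 = 11.2.

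**3. Recalculation with 20 equal centres (m = 5.6).**
- DE = 1 + 0.056 × 4.6 = 1.258
- PKT SD = 13 × √1.258 = 14.6
- n = 86 per group (t-based, surgical SD 14.38 unrounded; 87 if it is rounded to 14.4)
- 86/0.85 = 101.2, so 102 randomised per group
- Power with 95 analysed per group: about 93%, against 90% planned

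With m = 4.75 the design effect is 1.21, n is 85, and power at 95 is again about 93%.

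**4. Unequal centres.** With centre sizes of coefficient of variation CV, DE = 1 + ICC × ((1 + CV²) × m − 1). The protocol gives no CV, so the values below are assumptions. They use 20 sites, m = 5.6 and t-based n.

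| Assumed CV | DE | n per group | Power at 95 |
|---|---|---|---|
| 0 | 1.26 | 86 | 93% |
| 0.3 | 1.29 | 87 | 92% |
| 0.5 | 1.34 | 89 | 92% |
| 0.7 | 1.41 | 92 | 91% |

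To reach 1.504 with m = 5.6, (1 + CV²) × 5.6 must equal 10, so CV = √(10/5.6 − 1) = 0.89. With m = 4.75 it would be 1.05. With 15 sites (m = 7.47) and CV 0.5, DE is 1.47 and n is 94.

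**The case against.** The strongest defence is that nothing is miscalculated. The 10 is introduced as a supposition, the site count is approximate, and the result is on the safe side. Centres will also differ in size: section 3 opens at least 5 sites in a 9-month pilot and invites others later. At a fixed number of sites, 5.6 equal patients per centre is therefore the most favourable case, not the natural planning value. Most of this stands. This is an unreconciled pair of assumptions rather than an arithmetic slip, and putting 5.6 into the formula without more would replace a cautious figure with an optimistic one. It does not remove the point: approximately 20 does not stretch to 11, a CV near 0.89 is a strong assumption that should be stated if it is meant, and the formula used is the one for equal clusters.

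Three stronger readings are tempting, and the documents do not support them.

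- **The arms are computed on different bases.** A reader might notice that the two-arm total per site is 224/20 = 11.2, close to 10, and infer that a two-arm count was used for PKT and a one-arm count for surgery. But two surgeons per centre at 5 patients each also gives 10, with both counts per arm and about 11 centres. The protocol does not decide between these.
- **The trial is short of power.** Changing the cluster size alone raises the calculated power. Any figure below 90% would have to come from the separate discrepancy over the baseline correlation.
- **The sample size could be cut to about 102 per group.** That figure holds only for equal centres and for the correlation actually used in the calculation.

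**Conclusion.** The inconsistency is real: the cluster size behind the PKT design effect does not fit the number of sites planned, and the protocol states nothing that reconciles them. On the protocol's other inputs, the required number analysed per group is 86 with 20 equal centres and 87 to 92 with assumed CVs of 0.3 to 0.7, against 95 stated. Power at 95 per group is about 93% and about 92% to 91% respectively, against 90% planned.

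These figures rest on the adjusted SD of 13, an ICC of 0.056 in both arms, a difference of 7.2, 5 patients per surgeon and 20 sites. Taken alone, the mismatch is conservative and does not underpower the trial. Severity is low: section 9.1 needs clearer text, and the design need not change.

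**What to change.** In section 9.1, reconcile the PKT cluster size with the number of sites now expected. State the mean PKT patients per centre and the assumed variation in centre size, use DE = 1 + ICC × ((1 + CV²) × m − 1), and restate the PKT SD and the power for the fixed 224. If 10 is to be kept, say what supports it: about 11 sites, with section 4.1 brought into line, or a CV near 0.89 at 20 sites.

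Make the change in the same revision that resolves the baseline correlation, which section 9.1 gives as 0.25 in words while calculating with ρ = 0.5. Both feed the same SD, so the restated power should reflect both corrections together.

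The cost is a few sentences and one recalculation. Recruitment does not change.

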9.2 Proposed statistical analyses

Our primary analysis will compare the KOOS at the 24-month follow-up, between the randomised treatment arms, using a linear mixed model adjusting for surgeon as a random effect. Clustering in the surgical and non-surgical arms will be considered according to the recommended method (51) and as detailed in the sample size calculation. There are no pre-planned subgroup analyses, and no pre-planned formal interim analyses. Analysis of secondary outcomes will follow similar methods to those proposed for the primary analysis, where the data are of an appropriate form. Full details will be held in a separate detailed statistical analysis plan, and will be finalised prior to the database being locked at the end of follow up for final analysis. We are expecting a very low amount of missing data for the scales (~10% of our primary outcome) and will perform a complete case analysis. Our primary analysis will be based on intention-to-treat, but a complier average causal effect (CACE) analysis will also be performed as a sensitivity analysis. The statistical aspects of this trial will follow the Standard Operating Procedures of ECTU.

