2.2 ENDPOINTS

The primary and secondary endpoints will be captured within the following framework: **Population** - NHS patients <60 years with symptomatic knee OA localised to the medial compartment in whom surgical intervention is indicated. **Intervention** - Surgery with medial opening wedge HTO followed by standard postoperative rehabilitation based on local pathways. **Comparator** - Non-surgical intervention with Personalised Knee Therapy (PKT) delivered within an NHS physiotherapy department.

Primary endpoint

The primary outcome is the composite 24-month Knee Injury and Osteoarthritis Outcome Score (KOOS) score (www.koos.nu).

Secondary endpoints

1. Minimum requirements/acceptable variation (MRAV) proforma completed between 6 -12 months post intervention (note that this interval may be different from the same period post-randomisation due to NHS waiting lists)
2. KOOS composite score 12 months post-randomisation.
3. Five separate KOOS subscales at 12 and 24-months post randomisation.
4. Oxford Knee score (OKS, www.innovation.ox.ac.uk) at 12 and 24- months post-randomisation (46).
5. Forgotten Joint Score-12 (FJS-12, www.forgotten-joint-score.info) at 12 and 24-months post-randomisation (47,48).
6. EuroQol EQ-5D-5L score ([EQ-5D-5L – EQ-5D \(euroqol.org\)](http://EQ-5D-5L - EQ-5D (euroqol.org))) (49)
7. Pittsburgh Sleep Problem Scale at 12 and 24-months post randomisation (32)
8. Return to Work/Employment Questionnaire (9,10).

9. Additional study-knee related operative intervention at 12 and 24-months post randomisation

10. Intraoperative and postoperative complications 12 and 24 months post-randomisation

11. Health Economic Evaluation Outcomes

- a. Health and social care resource utilisation and associated NHS and PSS cost and Quality Adjusted life years (QALY) at 24 months
- b. Incremental Cost per QALY at 24 months
- c. NHS and PSS cost, and QALYs as modelled over a lifetime horizon to account for future impacts on the need for TKR and associated revision surgery and their timing relative to retirement
- d. Incremental Cost per QALY as modelled over a lifetime horizon to account for future impacts on the need for TKR and associated revision surgery and their timing relative to retirement.

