3 STUDY DESIGN

MOTION is a multi-centre, prospective randomised open blinded endpoint (PROBE) parallel-group controlled trial. Patients will be randomly assigned to one of the two treatment arms, in a 1:1 ratio, centrally, by the Edinburgh Clinical Trials Unit (ECTU) via a web-based system. To ensure groups are balanced, a minimisation algorithm will incorporate age, sex, body mass index and baseline KOOS score. Patients will be randomised to either the surgical intervention of High Tibial Osteotomy (HTO) or non-surgical intervention of Personalised Knee Therapy (PKT).

Included: Patient <60 years with symptomatic medial compartment knee OA who the treating orthopaedic surgeon considers a suitable candidate for medial opening wedge HTO

Enrollment

Excluded:

- Not meeting inclusion criteria
- Declined to participate
- Due to exclusion criterion

Randomized 1:1 (n=224)

Allocation

Allocated to non-surgical treatment – Personalised Knee Therapy (n=112)

- Detail those who received allocated intervention
- Detail those who did not receive allocated intervention (give reasons)

Intervention delivered within NHS according to local protocols

Allocated to surgical treatment – High Tibial Osteotomy (n=112)

- Detail those who received allocated intervention
- Detail those who did not receive allocated intervention (give reasons)

Intervention delivered within NHS according to local protocols

Follow-Up

Lost to follow-up (give reasons)

Discontinued intervention (give reasons)

Analyses

Analysed

- Excluded from analysis (give reasons)

6-12 months post-intervention: Minimum requirements and acceptable variation

12 months post-randomisation: KOOS, FJS, OKS, EQ5D-3L, Sleep Problem Scale, Return to Work, Additional operative intervention in study knee, Complications, Health Economic Evaluation

24 months post-randomisation: KOOS, FJS, OKS, EQ5D-3L, Sleep Problem Scale, Return to Work, Additional operative intervention in study knee, Complications, Health Economic Evaluation

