The within trial analysis (component 1) will describe rates of resource use, associated cost, and health utility scores/QALYs, will be presented contextually as summary statistics for each trial arm, with comparisons of total cost and QALYs undertaken Generalised Linear Modelling to account for anticipated skew (55) Incremental cost per QALY will be estimated by appropriate technique with preference given a recycled predictions approach (56) if data permits. The proportion of patients changing employment status will be examined using logistic regression.

Missing data will be imputed using appropriate techniques depending on degree of missingness, most likely multiple imputation by chained equations (which is considered gold standard in this area (57)). It is however worth noting that the most important cost factors relate to inpatient readmission and outpatient activity, will be obtained from medical records thus are not anticipated be prone to missingness.

Longer run cost-efficiency in terms of incremental cost per QALY will be examined by means of decision analytic simulation modelling (Component 2), This will extrapolate patient outcomes over a lifetime horizon to account for future impacts on the need for TKR and associated revision, and their timing relative to retirement since these often have significant impacts on employment potential and related. Initial scoping suggests this to be at least achievable Markov modelling, though as available data appear to be rich, more sophisticated options will be explored as needed. Initially reporting from the model will utilise the 24-month trial data, complimented with NJR and KOR data on longer term rates of TKR, revision TKR, and associated EQ-5D utility scores, a recent Cochrane review (12), topped up to date of analysis, and parameters extracted from a similar model (58). Additional, potentially non-systematic, targeted literature searches may be necessary for specific parameters if not available from these sources.

Uncertainty around both within trial and modelled ICERs will be presented using PSA with cost-effectiveness acceptability curves (CEAC) generated. Should the model prove inconclusive, value of information analysis will be undertaken to identify critical parameters which are driving overall uncertainty in decision criteria to inform follow up research potentially using the data linkage permissions obtained at consent.

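### The protocol fixes a complete-case primary analysis of 24-month KOOS that leaves the 12-month KOOS unused for participants who miss the final questionnaire

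*Protocol*

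**What the plan says.** Protocol section 9.2 sets the primary analysis as a comparison of 24-month KOOS between randomised arms, in a linear mixed model with surgeon as a random effect, by intention to treat. On missing outcomes it gives an expected rate and a method: "10% of our primary outcome) and will perform a complete case analysis". The only sensitivity analysis it names is the complier average causal effect, which deals with non-adherence and not with missing scores. Further detail is left to a separate SAP.

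The same instrument is collected a year earlier. Section 2.2 lists as a secondary endpoint the "KOOS composite score 12 months post-randomisation", and Table 2 in section 6 schedules it for every participant. Section 9.2 gives it no role in the primary model.

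Section 9.1 sizes the trial with its own allowance: "Allowing for 15% loss to follow up gives 112 per group". Section 9.3 says that missing data in the economic evaluation will be handled by a method chosen according to the degree of missingness, "most likely multiple imputation by chained equations".

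**The concern.** A complete-case analysis of one time point removes everyone without a 24-month KOOS, including those whose 12-month KOOS is already in the database. Adjusting for baseline protects the estimate only if, given arm and baseline, being missing is unrelated to the 24-month score. That is doubtful here. Participants know their treatment (section 3), the outcome is self-reported, and sections 6 and 7 collect it by email, post, telephone or portal with at most two reminders. How the knee was doing at 12 months could well influence who replies at 24 months, and not necessarily in the same way after surgery as after physiotherapy.

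At stake is bias in the primary estimate that data already held could remove. The method is stated in the protocol, with its justification, so it is not a detail left open for the SAP.

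**Working it through.** **1. The plan's own sample size.** The inputs from section 9.1 are: "Using 90% power, 2-sided $p=0.05$, with a difference of 7.2, and standard deviations of 14.4 and 15.9".

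- Average SD = √((14.4² + 15.9²)/2) = √230.1 = 15.17.
- n per group = 2 × (15.17 × (1.960 + 1.282)/7.2)² = 93.3, so 94 by the normal approximation. The noncentral t gives 95 (power 0.9023 at 95, 0.8993 at 94). The protocol states that "this gives a sample size of 95 per group".
- 95/(1 − 0.15) = 111.8, so 112 per group and 224 in total.

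The stated figures reproduce.

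**2. Who leaves a complete-case analysis.**

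- At 10% missing: 0.10 × 224 = 22 participants leave, about 101 per arm remain, and power is 92.1%.
- At 15% missing: 0.15 × 224 = 34 participants leave, about 95 per arm remain, and power is 90.6%.

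Power = Φ(7.2/(15.17 × √(2/n)) − 1.960), with n = 100.8 or 95.2. Power is adequate at either rate, so the issue is bias.

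**3. Bias when dropout follows the 12-month score.** The documents give neither a 12-to-24-month correlation nor a missingness mechanism, so both are assumed:

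- KOOS SD is 15 at each time, and baseline correlates 0.5 with each follow-up score. Section 9.1 gives the SD of 15 and uses ρ = 0.5 in its variance formula.
- The 12-to-24-month correlation r is 0.5 to 0.8.
- In one arm, the log-odds of a missing 24-month score rise by 0.5 or 1.0 for each SD by which the 12-month KOOS is lower (odds ratio 1.6 or 2.7).

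Simulated bias of the baseline-adjusted complete-case difference, in KOOS points (range over the two slopes):

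| r | 10% missing | 15% missing |
|---|---|---|
| 0.5 | 0.2 to 0.4 | 0.3 to 0.5 |
| 0.8 | 0.4 to 0.7 | 0.6 to 1.1 |

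As a share of 7.2, the extremes are 0.19/7.2 = 3% and 1.08/7.2 = 15%. The affected arm's mean is too high. The HTO benefit is understated if that arm is PKT and overstated if it is HTO. The bias is the same when the other arm loses an equal fraction at random, so equal dropout rates are no safeguard. If all dropouts have a 12-month KOOS, predicting the missing scores from baseline and 12-month KOOS within arm brings the bias to zero within simulation error (under 0.04 points).

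**4. Precision gained.**

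- Partial correlation given baseline = (r − 0.25)/(1 − 0.25), taking 0.5 for both baseline correlations. For r = 0.7 this is 0.45/0.75 = 0.6.
- Effective n = 112(1 − m)/(1 − 0.6² × f), where m is the fraction missing and f is the share with only a 12-month score among those who have one.
- At m = 0.15 with all dropouts having a 12-month score, f = 0.15 and n = 95.2/0.946 = 100.6. With half having one, f = 0.075/0.925 = 0.081 and n = 95.2/0.971 = 98.1. The gain is about 3 to 5 participants per arm.
- Over r = 0.5 to 0.8, m = 0.10 or 0.15, and half or all dropouts with a 12-month score, power rises by 0.15 to 2.15 percentage points.

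**The case against.** The strongest reply is that the case for differential loss is speculative. Both arms are followed centrally, remotely and on the same schedule. A dissatisfied PKT participant can cross over to surgery, which section 9.1 expects for 20% of that arm, and remain in follow-up. The 12-month KOOS is not wasted either, since it is analysed as a secondary endpoint. Only participants with a 12-month but no 24-month score are affected, and their number is unknown. All of this stands, and it limits the point to robustness under mechanisms that are plausible but unproven.

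A reader might also infer more than the documents support:

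- **That 10% and 15% conflict.** Section 9.1 gives a sample-size allowance and section 9.2 an expectation. Setting the allowance above the expected loss is ordinary prudence, and power holds at either rate. Nothing in the text says the two losses are to be added together.
- **That complete case is not intention to treat.** The protocol uses that term for analysis as randomised despite crossover, and contrasts it with the CACE analysis. Complete cases analysed by randomised arm fit that usage.
- **That the economic analysis is inconsistent.** Costs and QALYs are different quantities built from many items, under a separate plan. Imputing them is no contradiction.
- **That the bias could be put at 0.5 to 1.5 points.** That follows from assuming 20% missing in PKT, 10% in HTO, and missing scores 5 to 15 points worse: (0.10 − 0.20) × 5 to 15 = −0.5 to −1.5. In that scenario the HTO benefit is understated. A gap that the 12-month score does not explain would also survive the model proposed here.

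**Conclusion.** The point holds as a robustness weakness that should be corrected. The protocol commits its primary outcome to complete cases although an intermediate measurement of the same score is available, and it names no analysis of how missing scores might affect the result. If dropout in one arm follows the 12-month KOOS, the bias is about 0.2 to 0.7 points at 10% missing and 0.3 to 1.1 at 15% (3% to 15% of 7.2). These figures rest on the assumed odds ratios and correlations, and on dropout being score-related in one arm only. The actual size is unknown. If missingness and its relation to the score are alike in both arms, the net shift is small. Power is not a reason for the change.

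**What to change.** Replace the complete-case sentence in section 9.2 with one of two primary analyses:

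- a likelihood-based repeated-measures mixed model of 12- and 24-month KOOS, with baseline KOOS as covariate, arm-by-time terms and the clustering already planned, taking the 24-month contrast as primary; or
- multiple imputation by arm that includes the 12-month KOOS, followed by the planned 24-month model.

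Either way, let the relation between the 12- and 24-month scores differ by arm. Section 6 notes that waiting lists separate the time since intervention from the time since randomisation, so a 12-month score after delayed surgery may predict the 24-month score less well.

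Keep complete case as a sensitivity analysis. An arm-specific delta-adjusted analysis is a sensible addition to the SAP, because neither primary option removes bias from dropout that depends on the unseen 24-month score. Its absence from the protocol is not itself a fault.

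The cost is a change of wording in the protocol and SAP and modest extra modelling, including care that the model converges with clustering and arm-specific covariance. No new data are needed, N stays at 224, and section 9.2 allows the SAP to be finalised up to database lock.
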